10.6.2 Other Observations Related to Safety

10.6.2.1 IDDD Performance

IDDD safety and performance will be summarized in detail for patients implanted with the SOPH-A-PORT Mini S. Difficulties associated with the implant procedure (e.g. excessive bleeding, CSF leakage, etc.) will be summarized. A summary of abnormal findings from the IDDD radiological assessments will also be presented.

The proportion of patients with at least one IDDD failure and/or malfunction, as well as the number of and reasons for IDDD failures/malfunctions and actions taken will be summarized. The rate of IDDD failures/malfunctions and 95% confidence interval will also be estimated. The time from initial implant surgery to first IDDD failure and/or malfunction will be summarized. Patients without an IDDD failure/malfunction will be censored at their last study drug injection date. A by-patient listing of the device failure/malfunction data will be displayed.

The proportion of patients for whom a successful first injection of study drug occurred will be reported among those for whom a first injection was attempted (i.e. those who had an apparently successful implantation and did not suffer a device removal or revision prior to first scheduled injection). The proportion of patients who had no failed injection attempts during the study will also be summarized. The corresponding 95% confidence intervals of the proportion of interest will be estimated, where appropriate. Injections not given for patient reasons (e.g. patient uncooperative, competing medical issue, etc) will not be included in the determination of these success proportions. The frequency and reasons for unsuccessful injection attempts will be reported.

10.6.3 Secondary Analysis

10.6.3.1 Clinical Assessments

The change from baseline in neurocognitive assessment based scores will be examined by dose group. Furthermore, the effect of HGT-1410 administration on QoL measures will be examined by presenting mean change from baseline by dose groups. Other relevant assessments which might help in the understanding of clinical activity will also be analyzed.

10.6.3.2 Pharmacodynamic Analyses

To determine the effects of HGT-1410 administration on biomarkers, mean change from baseline will be assessed at selected time points. The heparan sulfate reduction (in CSF and urine) will be examined using mean change and the corresponding 95% confidence interval. The concentration of inflammatory cytokines in serum and CSF will also be examined. Other exploratory biomarkers in CSF, serum, and urine may also be examined.

The effect of anti- rhHNS antibodies on the changes in CSF biomarkers may also be examined by presenting summary tables by antibody status.

The planned analyses and presentations will be defined in the Statistical Analysis Plan (SAP).

11 ADMINISTRATIVE CONSIDERATIONS

11.1 Investigators and Study Administrative Structure

Before initiation of the study, the Investigators must provide the Sponsor with a completed Form Food and Drug Administration (FDA) 1572 or Investigator Agreement. Study medications may be administered only under the supervision of the Investigators listed on this form. Curriculum vitae must be provided for the Investigators and sub-investigators listed on Form FDA 1572 or Investigator Agreement.

The Investigator should ensure that all persons assisting with the study are adequately informed about the protocol, any amendments to the protocol, the study treatments, and their study related duties and functions. The Investigator must maintain a list of sub-investigators and other appropriately qualified persons to whom he or she has delegated significant study related duties.

11.2 Institutional Review Board or Independent Ethics Committee Approval

Before initiation of the study, the Investigator must provide the Sponsor with a copy of the written IRB or IEC approval of the protocol and the informed consent form. This approval must refer to the informed consent form and to the study title, study number, and version and date of issue of the study protocol, as given by the Sponsor on the cover page of the protocol.

Status reports must be submitted to the IRB/IEC at least once per year. The IRB/IEC must be notified of completion of the study. Within 3 months of study completion or termination, a final report must be provided to the IRB/IEC. A copy of these reports will be sent to the study clinical monitor. The Investigators must maintain an accurate and complete record of all submissions made to the IRB/IEC, including a list of all reports and documents submitted. AEs which are reported to the US FDA or other Regulatory agencies (Investigational New Drug [IND] Safety Reports) must be submitted promptly to the IRB/IEC.

11.3 Ethical Conduct of the Study

The procedures set out in this study protocol, pertaining to the conduct, evaluation, and documentation of this study, are designed to ensure that the Sponsor and Investigators abide by good clinical practice (GCP) as described in the 21 CFR Parts 50, 56, and 312 and the International Conference on Harmonization (ICH) GCP Guidelines.

11.4 Patient Information and Consent

Before enrolling in the clinical study, the patient's parent(s), or the patient's legally authorized representative(s) must consent to participate after the nature, scope, and possible consequences of the clinical study have been explained in a form understandable to him or her. An informed consent form that includes information about the study will be prepared and given to the patient's parent(s), or the patient's legally authorized representative(s). This document will contain all FDA and ICH-required elements.

The informed consent form must be in a language understandable to the patient's parent(s), or the patient's legally authorized representative(s) and must specify who informed the patient's parent(s) or the patient's legally authorized representative.

After reading the informed consent document, the patient, patient's parent(s), or the patient's legally authorized representative(s) must give consent in writing. The patient's consent must be confirmed at the time of consent by the personally dated signature of the patient, patient's parent(s) or the patient's legally authorized representative(s) and by the personally dated signature of the person conducting the informed consent discussions. If the patient, patient's parent(s), or the patient's legally authorized representative(s) is unable to read, oral presentation and explanation of the written informed consent form and information to be supplied must take place in the presence of an impartial witness. Consent (or assent) must be confirmed at the time of consent orally and by the personally dated signature of the patient, patient's parent(s) or by the patient's legally authorized representative(s). The witness and the person conducting the informed consent discussions must also sign and personally date the informed consent document. It should also be recorded and dated in the source document that consent was given.

A copy of the signed and dated consent document(s) must be given to the patient's parent(s), or the patient's legally authorized representative(s). The original signed and dated consent document will be retained by the Investigator.

The Investigator will not undertake any measures specifically required solely for the clinical study until valid consent has been obtained.

A model of the informed consent form to be used in this study will be provided to the sites separately from this protocol.

Where applicable, signed assent(s) to participate in the study must be obtained.

11.5 Patient Confidentiality

Patient names will not be supplied to the Sponsor. Only the patient number and patient initials will be recorded in the eCRF, and if the patient name appears on any other document, it must be obliterated before a copy of the document is supplied to the Sponsor. Study findings stored on a computer will be stored in accordance with local data protection laws. The patients will be told that representatives of the Sponsor, a designated CRO, the IRB/IEC, or regulatory authorities may inspect their medical records to verify the information collected, and that all personal information made available for inspection will be handled in strictest confidence and in accordance with local data protection laws. The Investigator will maintain a personal patient identification list (patient numbers with the corresponding patient names) to enable records to be identified.

11.6 Study Monitoring

Monitoring procedures that comply with current GCP guidelines will be followed. On-site review of the eCRFs for completeness and clarity, cross-checking with source documents, and clarification of administrative matters will be performed.

The study will be monitored by the Sponsor or its designee. On site monitoring will be performed by a representative of the Sponsor (Clinical Study Monitor) who will review the CRFs and source documents. The site monitor will ensure that the investigation is conducted according to protocol design and regulatory requirements by frequent site visits and communications (letter, telephone, and facsimile).

11.7 Case Report Forms and Study Records

Case report forms are provided for each patient in electronic format. Electronic Data Capture (EDC) will be used for this study. The study data will be recorded from the source documents into the eCRF. The electronic files will be considered as the CRFs.

All forms must be filled out by authorized study personnel. All corrections to the original eCRF entry must indicate the reason for change. The Investigator is required to sign the eCRF after all data have been captured for each patient. If corrections are made after review and signature by the Investigator, he or she must be made aware of the changes, and his or her awareness documented by re-signing the eCRF.

11.7.1 Critical Documents

Before Shire HGT initiates the trial (ie, obtains informed consent [assent if applicable] from the first patient), it is the responsibility of the Investigator to ensure that the following documents are available to Shire HGT or their designee:

- Curricula vitae of Investigator and sub-investigator(s) (current, dated and signed or supported by an official regulatory document)
- Current medical license of Investigator and sub investigator(s)
- Signed and dated agreement of the final protocol
- Signed and dated agreement of any amendment(s), if applicable
- Approval/favorable opinion from the IRB/IEC clearly identifying the documents reviewed: protocol, any amendments, Patient Information/Informed Consent Form (Assent form if applicable), and any other written information to be provided regarding patients recruitment procedures
- Copy of IRB/IEC approved Patient Information/Informed Consent Form (Assent Form if applicable)/any other written information/advertisement
- Any additional regulatory approvals, ie national regulatory approvals
- List of IRB/IEC Committee members/constitution
- Financial agreement(s)
- Documentation from central or local laboratory as applicable
 - Reference ranges
 - Certification/QA scheme/other documentation

Regulatory approval and notification as required must also be available; these are the responsibility of Shire HGT. All trial documents will be available in a Trial Master File (TMF) at the Investigator/trial site and at Shire HGT.

11.8 Device Failure Adjudication Process

The final cause for device failures will be adjudicated by a Shire team by examining the clinical database, safety database, and manufacturer investigation of returned devices.

11.9 Protocol Violations/Deviations

The Investigator will conduct the study in compliance with the protocol. The protocol will not be initiated until the IRB/IEC and the appropriate regulatory authorities have given approval/favorable opinion. Modifications to the protocol will not be made without agreement of the Sponsor. Changes to the protocol will require written IRB/IEC approval/favorable opinion prior to implementation, except when the modification is needed to eliminate an immediate hazard(s) to patients. The IRB/IEC may provide, if applicable regulatory authorities permit, expedited review and approval/favorable opinion for minor change(s) in ongoing studies that have the approval/favorable opinion of the IRB/IEC. The Sponsor will submit all protocol modifications to the regulatory authorities in accordance with the governing regulations. A record of patients screened, but not entered into the study, is also to be maintained. There will be no protocol exemptions granted for this study.

When immediate deviation from the protocol is required to eliminate an immediate hazard(s) to patients, the Investigator will contact the Sponsor or its designee, if circumstances permit, to discuss the planned course of action. Any departures from the protocol must be fully documented as a protocol deviation. Protocol deviations will need to be reviewed by the medical monitor and may also be required to be submitted to the IRB/IEC.

Protocol modifications will only be initiated by the Sponsor and must be approved by the IRB/IEC and submitted to the FDA or other applicable international regulatory authority before initiation.

11.10 Access to Source Documentation

Regulatory authorities, the IEC/IRB, or the Sponsor may request access to all source documents, CRFs, and other study documentation for on-site audit or inspection. Direct access to these documents must be guaranteed by the Investigator, who must provide support at all times for these activities. Monitoring and auditing procedures that comply with current GCP guidelines will be followed. On-site review of the CRFs for completeness and clarity, crosschecking with source documents, and clarification of administrative matters will be performed.

11.11 Data Generation and Analysis

The clinical database will be developed and maintained by a contract research organization or an electronic data capture technology provider as designated by Shire HGT. Shire HGT or its designee will be responsible for performing study data management activities.

Adverse events will be coded using MedDRA. Concomitant medication will be coded using WHO-DD. Centralized laboratories will be employed as described in the study manual to aid in consistent measurement of efficacy and safety parameters.

11.12 Premature Closure of the Study

11.12.1 Study Termination

If the Sponsor or an Investigator discovers conditions arising during the study which indicate that the clinical investigation should be halted due to an unacceptable patient risk, the study may be terminated after appropriate consultation between Shire HGT and the Investigators. In addition, a decision on the part of Shire HGT to suspend or discontinue development of the study material may be made at any time.

11.12.2 Site Termination

A specific site may be terminated separate from the general study for, but not limited to, the following conditions:

- The discovery of an unexpected, significant, or unacceptable risk to the patients enrolled at the site.
- Failure of the Investigator to enter patients at an acceptable rate.
- Insufficient adherence by the Investigator to protocol requirements.

11.13 Retention of Data

Essential documents should be retained until at least 2 years after the last approval of a marketing application and until there are no pending or contemplated marketing applications or at least 2 years have elapsed since the formal discontinuation of clinical development of the investigational product. The Sponsor will notify the Investigator if these documents must be retained for a longer period of time. It is the responsibility of the Sponsor to inform the Investigator or institution as to when these documents no longer need to be retained.

Biological samples may be reserved for potential, future, biomarker studies (see Section 7.7.6).

11.14 Financial Disclosure

The Investigator should disclose any financial interests in the Sponsor as described in 21 CFR Part 54 prior to beginning this study. The appropriate form will be provided to the Investigator by the Sponsor, which will be signed and dated by the Investigator, prior to the start of the study.

11.15 Publication and Disclosure Policy

All information concerning the study material, such as patent applications, manufacturing processes, basic scientific data, and formulation information supplied by the Sponsor and not previously published are considered confidential and will remain the sole property of the Sponsor. The Investigator agrees to use this information only in accomplishing this study and will not use it for other purposes.

It is understood by the Investigator that the information developed in the clinical study may be disclosed as required to the authorized regulatory authorities and governmental agencies.

In order to allow for the use of the information derived from the clinical studies, it is understood that there is an obligation to provide the Sponsor with complete test results and all data developed in the study in a timely manner.

The Investigator and any other clinical personnel associated with this study will not publish the results of the study, in whole or in part, at any time, unless they have consulted with Shire HGT, provided Shire HGT a copy of the draft document intended for publication, and obtained Shire HGT's written consent for such publication. All information obtained during the conduct of this study will be regarded as confidential. Shire HGT will use the information for registration purposes and for the general development of the drug.

Appendix 1 Schedule of Events

Table A1-1 HGT-SAN-067 Study Assessments for Patients Who Have Received 6 Months of HGT-1410 Treatment in Study HGT-SAN-055

Assessment	Screening/or HGT-SAN-055 EOS Visit ^k (Month 6 from the start of HGT-SAN-055)	Dosed every 28 (±7) days (ie, Q4W)		Months 12, 24, 36, and 54 (from the start of HGT-SAN-055)	EOS ^f Month 55 (from the start of HGT-SAN-055)	Month 56 Safety Follow-up ^j
		Pre-Tx Day 1 ^a	IT dosing Day 2 (±2)			
Informed Consent/Enrollment		•				
Physical Examination	•	•	•		•	
Height and Weight	•	•			•	
Head Circumference	•			•	•	
Visual and Hearing Assessment				•	•	
ECG	•		• ^b		•	
Vital Signs	•	•	•		•	
Hematology	•	•			•	
Serum Chemistry	•	•			•	
Pregnancy Testing ⁿ	•	•				
Urinalysis	•	•			•	
Leukocyte pellet preparation ^o	•					
Urine Heparan Sulfate and Heparan Sulfate Derivatives	•			• ^e	•	
Plasma and serum Heparan Sulfate and Heparan Sulfate Derivatives	•			• ^e	•	
Anti-rhHNS antibody testing (serum and CSF) ^l	•			•	•	
Auditory Brainstem Response (ABR)	•			•	• ^p	
MRI of the Head	•			•	• ^p	
CSF Sample Collection ^m	•		• ^c		• ^{c, p}	
HGT-1410 dosing: every 28 (±7) days ^{d, g,}			•			
Neurological Examination ^h	•	•	•		•	
Full Neurodevelopmental Testing ⁱ	•			•	•	
Children's Sleep Habits Rating Scale	•			•	•	

Table A1-1 HGT-SAN-067 Study Assessments for Patients Who Have Received 6 Months of HGT-1410 Treatment in Study HGT-SAN-055

Assessment	Screening/or HGT-SAN-055 EOS Visit ^k (Month 6 from the start of HGT-SAN-055)	Dosed every 28 (±7) days (ie, Q4W)		Months 12, 24, 36, and 54 (from the start of HGT-SAN-055)	EOS ^f Month 55 (from the start of HGT-SAN-055)	Month 56 Safety Follow-up ^j
		Pre-Tx Day 1 ^a	IT dosing Day 2 (±2)			
Child Health Questionnaire-50	•			•	•	
Child Health Questionnaire-87	•			•	•	
Infant Toddler QOL Questionnaire	•			•	•	
Concomitant Medications, Therapies, and Procedures	•	•	•		•	•
Adverse Event Monitoring	•	•	•		•	•
X-ray examination of device (if treatment is to continue beyond end of study)					•	
Removal of IDDD				• ^q	• ^q	

Abbreviations: ABR = Auditory brainstem response; CSF = cerebrospinal fluid; EOS = end of study ; ECG = electrocardiogram; IT = intrathecal; MRI = Magnetic resonance imaging; TX = treatment

Note: The timing of assessments is calculated from the start of HGT-SAN-055. Therefore, for example, the end-of-study visit, as presented here at Month 54, corresponds to Month 48 in HGT-SAN-067, but represents a total of 54 months of study treatment (48 months in HGT-SAN-067 + 6 months in HGT-SAN-055).

^a Week 1 only, and only performed if >7 days have elapsed since HGT-SAN-055 EOS visit assessments.

^b ECG to be performed following administration of study drug.

^c CSF samples will be obtained according to the process with in the study operations manual). An attempt will be made to obtain a CSF sample via the IDDD prior to each administration of HGT-1410 and at the End of Study visit. If it is not possible to obtain a CSF using the IDDD, the IDDD may be replaced (up to twice in a 6 month period [including the time in the HGT-SAN-055 study]) or a LP may be performed (can occur up to 5 times in a 6 month period).

^d Patients may be discharged as early as 4 hours post HGT-1410 infusion (ie, on Day 2) when deemed clinically stable by the Investigator.

^e Specimens collected once a month, at Day 1 of the first treatment week.

^f All patients who complete the study will have end of study assessments performed 30 (±7 days) after their last dose of study drug.

^g If a patient's IDDD becomes nonfunctional or infected; it will be replaced (up to 2 times in a 6 month period; including the time in Study HGT-SAN-055).

^h The neurological exam should not occur sooner than 4 hours after administration of study drug or before the patient has fully recovered from any anesthesia administered for the dosing, whichever occurs later.

ⁱ Full neurodevelopmental testing includes an assessment with the Vineland Adaptive Behavior Scales, Second Edition (VABS-II)

^j A safety follow up telephone call will be made 30 (±7 days) after End of Study Procedures.

^k Assessments will be required only if more than 60 days have elapsed following the HGT-SAN-055 procedures. These assessments would be repeated within 30 days prior to the first scheduled HGT-1410 IT dose.

Table A1-1 HGT-SAN-067 Study Assessments for Patients Who Have Received 6 Months of HGT-1410 Treatment in Study HGT-SAN-055

Assessment	Screening/or HGT-SAN-055 EOS Visit ^k (Month 6 from the start of HGT-SAN-055)	Dosed every 28 (±7) days (ie, Q4W)		Months 12, 24, 36, and 54 (from the start of HGT-SAN-055)	EOS ^f Month 55 (from the start of HGT-SAN-055)	Month 56 Safety Follow-up ^j
		Pre-Tx Day 1 ^a	IT dosing Day 2 (±2)			

^k Blood sample drawn before IT injection of HGT-1410.

^m CSF will be tested for standard chemistries, heparan sulfate and heparan sulfate derivatives, anti-rhHNS antibodies, and MPS exploratory biomarkers.

ⁿ A pregnancy test will be carried out on pre-treatment Day 1 in females who are postmenarche to premenopause (childbearing). The results must be negative before study drug can be administered.

^o A blood sample for leukocyte pellet preparation is to be taken at baseline, before dosing. This pellet should be stored frozen, and will be used for additional disease-related laboratory studies, including possible assessment of cross-reactive immunologic material. If this is not drawn at baseline, it can be drawn at any subsequent visit, but it must be taken before dosing. This only needs to be taken once during the study.

^p These assessments are not to be performed at an EOS visit conducted at Month 55 if they were performed at the Month 54 visit

^q The IDDD will be removed at the Month 54 visit, or at the EOS visit if the patient discontinues the study prior to the Month 54 visit

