Enrolled patients will check in to the study center 1 day before each of the scheduled HGT-1410 dosing days for safety assessments (designated Day 1). If no safety concerns exist, the patient will subsequently receive IT administration of HGT-1410 on Day 2 (± 2 days). However, if feasible and there are no safety concerns in the opinion of the investigator, the Day 1 and Day 2 assessments may be combined and performed on Day 2; if this is done the results will be recorded as Day 2. Patients will remain in the study center for at least 4 hours following dosing with HGT-1410 and will be discharged from the unit when deemed clinically stable by the Investigator.

All patients will have received a series of standardized neurodevelopment assessments; in the HGT-SAN-055 study, these will have occurred at Baseline and either prior to or at the 6-month time point. Patients will continue in HGT-SAN-067 with whichever age specific assessment they began with in HGT-SAN-055. If, however, a patient's capability improves and they become capable of completing assessments at a higher level, such additional assessments may be

added. Any additional assessments are to be performed after the original assessments (those used in study HGT-SAN-055) have been carried out.

A MRI of the head and ABR testing will be performed at Months 12, 24, 36, and 54 (note that assessment time point nomenclature includes the 6 months in the HGT-SAN-055 study).

In the event of a device malfunction, X-rays may be performed to investigate, as well as to verify correct catheter and port placement following surgical IDDD implantation or revision. In addition, fluoroscopy may be employed intra-operatively to guide catheter placement. Patients may undergo 3 X-ray examinations in association with each episode of IDDD malfunction and subsequent IDDD revision or replacement. The number of IDDD revisions/replacements is limited to 2 in any 6-month period (including the time in the HGT-SAN-055 study), and the number of protocol-associated X-ray evaluations is limited to 6 exposures in any 6-month period (including time in study HGT-SAN-055). If patients are to continue to receive HGT-1410 using the IDDD beyond the duration of this study, they will also have X-ray examinations of the device performed at the EOS visit, to document correct positioning.

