7.13.2 X-ray Verification of Intrathecal Drug Delivery Device Placement

A postoperative x-ray check of the IDDD will be performed following surgery to verify proper installation and confirmation of IDDD placement at the mid-thoracic level. The x-rays may be performed to check placement of the device, as needed, throughout the study. If the patient is to receive intrathecal HGT-1410 beyond the end of the study, an X-ray will be performed at the end of the study to verify that the IDDD is in the correct position. At a minimum, the date of the x-ray verifying correct IDDD placement will be documented on the patient's eCRF. If the device requires revision or replacement during the study, additional x-rays will be taken to document proper positioning of the device. If an IDDD malfunctions, an X-ray may be performed to assess the potential cause of malfunction

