8.2.1.1 Day 1 (Pre-treatment) Assessments Performed Prior to Each Dose

- Physical examination
- Height and weight
- Vital signs
- Hematology
- Serum chemistry
- Urinalysis
- Pregnancy testing (applicable females only)
- Neurological examination (performed prior to the administration of anesthesia and the HGT-1410 IT injection)
- Concomitant medications, therapies, and procedures
- AE assessments

Note: If the HGT-SAN-055 EOS (or HGT-SAN-067 Screening) assessments were performed within 7 days of first intrathecal HGT-1410 treatment in this study, the pre-treatment assessments described in this section do not need to be completed prior to the first treatment in study HGT-SAN-067.

DAY 1 (PRE-TREATMENT) ADDITIONAL ASSESSMENTS PERFORMED AT MONTHS 12, 24, 36, AND 54

- Head circumference
- Visual and hearing assessments
- Urine heparan sulfate and heparan sulfate derivatives
- Plasma and /or serum heparan sulfate and heparan sulfate derivatives
- Anti-rhHNS antibody testing
- ABR
- MRI of the head
- Full neurodevelopmental testing, including VABS-II (performed prior to the administration of anesthesia and the HGT-1410 IT injection)
- Children's Sleep Habits Rating Scale
- Child health questionnaire-50
- Child health questionnaire-87
- Infant toddler QoL Questionnaire

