8.2.1.2 Day 2 (± 2 days) Assessments and Administration of HGT-1410

Patients may be discharged from the clinical site 4 hours after dosing, if deemed stable by the Investigator.

- Physical examination
- ECG (performed following IT study drug injection)
- Vital signs
- CSF sample collection (obtained prior to IT study drug injection)
- HGT-1410 IT injection (Day 2 ± 2 days)
- Neurological examination
- Concomitant medications, therapies, and procedures
- AE assessments

The neurological exam should not occur sooner than 4 hours after study drug administration or before the patient has fully recovered from any anesthesia administered for the dosing, whichever occurs later.

8.3 End of Study/Early Termination Procedures: Month 55

Patients who complete the study or who discontinue prior to the end of the study, will have EOS assessments performed 30 (± 7 days) after their last dose of HGT-1410.

Patients who discontinue or are withdrawn prior to study completion will be asked to participate in the EOS procedures at the time of discontinuation. Participation in these EOS procedures will be strongly encouraged, but is voluntary for those patients electing to discontinue from the study. Note: Patients will have the IDDD removed when they discontinue from the study, unless the patient is continuing to receive treatment through another mechanism (eg, expanded access, commercially available).

- Physical examination
- Height and weight
- Head circumference
- Visual and hearing assessment
- ECG
- Vital signs
- Hematology
- Serum chemistries
- Urinalysis
- Urine heparan sulfate and heparan sulfate derivatives
- Plasma and serum heparan sulfate and heparan sulfate derivatives
- Anti-rhHNS antibody testing
- ABR (unless performed at Month 54)
- MRI of the head (unless performed at Month 54)
- CSF sample collection (unless performed at Month 54)
- Neurological examination
- Full neurodevelopmental testing, including VABS-II
- Children's Sleep Habits Rating Scale
- Child health questionnaire-50
- Child health questionnaire-87
- Infant toddler QoL Questionnaire
- Concomitant medications, therapies, and procedures
- AE assessments
- X-ray of device, if the patient is to continue to receive intrathecal HGT-1410 beyond the end of the study

All patients who discontinue the study early will have their IDDD removed.

Patients who withdraw or discontinue after having received fewer than 3 IT injections will not need to complete the EOS visit.

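### The schedule orders the intrathecal device removed at Month 54 with no exception, yet X-rays it at Month 55 in patients who continue treatment

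*Protocol*

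**What the plan says.** Footnote q to the device-removal row of Table A1-1 (Appendix 1) reads: "The IDDD will be removed at the Month 54 visit, or at the EOS visit if the patient discontinues the study". The sentence ends by limiting the second branch to patients who leave before Month 54. That branch changes when the device comes out; it exempts nobody from removal. The wording is the same in the Amendment 4 and Amendment 5 versions of the table.

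Four places require the device to be imaged at end of study in patients who will stay on treatment:

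- Table A1-1, the row above removal, marked in the Month 55 column: "X-ray examination of device (if treatment is to continue beyond end of study".
- Section 4.1, on patients who will keep using the device after the study: "they will also have X-ray examinations of the device performed at the EOS visit, to document correct positioning".
- Section 7.13.2: "an X-ray will be performed at the end of the study to verify that the IDDD is in the correct position".
- The end-of-study procedure list in Section 8.3: "X-ray of device, if the patient is to continue to receive intrathecal HGT-1410 beyond the end of the study".

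The synopsis, Section 7.13.4 and the Note in Section 8.3 say that the device is removed when a patient discontinues from the study, unless treatment goes on by another route. The synopsis and Section 7.13.4 name an extension study, expanded access or commercial supply as examples.

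**The concern.** The X-ray exists to show that the device is correctly placed for further use, so it presupposes an implanted device. Footnote q takes that device out one visit earlier. The rule that would resolve the conflict is in the body text, but the schedule does not carry it, and Sections 4.1 and 7.1 send sites to the schedule.

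What is at stake is surgery in children. Under Section 7.13.1, implantation is done under general anesthesia. Section 6.3.3 offers lumbar puncture as the fallback and says that it too may need general anesthesia. Section 7.8 tries to combine procedures so as to limit such exposure. An avoidable explant followed by a re-implant works against that aim.

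**Working it through.** The plan states no figure to reproduce. The check sets the instructions side by side and then works out the intervals.

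**1. Are Month 54 and end of study different visits?** Three places point to separate visits.

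- Section 8.2.1.1 lists "ADDITIONAL ASSESSMENTS PERFORMED AT MONTHS 12, 24, 36, AND 54" under a pre-treatment heading, so Month 54 is a dosing visit.
- Footnote f: "All patients who complete the study will have end of study assessments performed 30" (±7) days after the last dose. Section 4.1 labels that visit Month 55.
- Footnote p: "These assessments are not to be performed at an EOS visit conducted at Month 55 if they were performed at the Month 54 visit". This makes sense only if the visits differ.

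One place points the other way. The Note under Table A1-1 speaks of the end-of-study visit as shown at Month 54, which conflicts with the table's own Month 55 column.

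**2. What happens to each type of patient?**

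| Patient | Footnote q | End-of-study X-ray | Compatible? |
|---|---|---|---|
| Leaves before Month 54, stops treatment | Remove at end-of-study visit | Not required | Yes |
| Completes, stops treatment | Remove at Month 54 | Not required | Yes |
| Completes, continues treatment | Remove at Month 54 | Required at Month 55 | No |

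**3. Does merging the visits help?** No. If Month 54 were the end-of-study visit, footnote q would still order removal, without exception, of a device whose position is being checked because it will stay in use.

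**4. Intervals for a continuing completer**, taking the last dose and the removal to fall at the Month 54 visit:

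- Removal to end-of-study X-ray, 30 (±7) days: 30 − 7 = 23 to 30 + 7 = 37 days.
- Removal to next dose, assuming that the follow-on route keeps the 28 (±7) day interval of Section 6.3: 28 − 7 = 21 to 28 + 7 = 35 days.

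**5. Number affected.** Section 5.1 caps enrolment at 12. The protocol does not say how many will continue, so the range is 0 to 12.

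**The case against.** The strongest reply is that the intent is not in doubt. The retention rule appears three times, including in the section devoted to device removal, and the X-ray row sits directly above the removal row. A site would have to overlook all of this to explant a working device from a child it knows is continuing. Discontinuing from the study can also be read as leaving it for any reason: Section 8.3 opens by addressing completers and early leavers together, and an extension study is one of the examples of continued treatment. On this view, footnote q is leftover wording, and the Note that puts end of study at Month 54 points the same way.

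Much of this stands. The harm depends on a site following the footnote over the body text, the number affected may be zero, and this is an internal inconsistency rather than a deliberate choice of design. The document at hand is also only part of a larger file, so Amendment 5 is simply the latest version shown.

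The reply does not remove the conflict. Completers are covered by the body text only through interpretation, the text shown does not say that the body overrides the schedule, and the loose Note leaves the footnote's unconditional order in place.

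**Conclusion.** The concern holds. For a patient who completes the study and continues intrathecal HGT-1410, footnote q and the end-of-study X-ray cannot both be carried out.

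In size, this concerns 0 to 12 patients, with removal about 23 to 37 days before the X-ray. If the footnote is followed and port delivery later resumes, the cost is one explant and one re-implant per patient. The 23 to 37 day figure rests on Month 55 being the end-of-study visit and on the last dose falling at Month 54. The 21 to 35 day figure for the next dose rests on the assumed follow-on interval.

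No endpoint or analysis is affected. It should still be fixed, because it is an operative surgical instruction that is wrong as written for these patients.

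**What to change.** Add an exception to footnote q, for example: *except where intrathecal HGT-1410 will go on after the study under another mechanism*.

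In the synopsis, Section 7.13.4 and the Note in Section 8.3, extend the wording from patients who discontinue to patients who complete or discontinue, so that completers no longer depend on interpretation.

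As a secondary consistency edit, the same exception could go into the removal statements in Section 4.1, Section 7.27 and the closing lines of Section 8.3. Those deal with early leavers or a sponsor stop and do not create the Month 54 conflict.

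The cost is one clause in one footnote and one phrase in three places, plus the same clause in three further places if the secondary edit is made. No procedure is added.
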